9. SAFETY REPORTING

Vital signs, physical examinations, or other safety-relevant data observed at screening, baseline, during the course of the study and at the end-of-study evaluation will be assessed with regard to possible changes compared to findings before start of treatment.

Laboratory data will be analysed both quantitatively as well as qualitatively. The latter will be done via comparison of laboratory data to their reference ranges. Values outside the reference range as well as values defined as clinically relevant will be summarised.

9.1. Definition of Serious Adverse Events

A serious adverse event is any untoward medical occurrence that:

- results in death
- is life-threatening

Principal Investigator:	[name]	IRAS ID	252047
Short Title:	Ox-FAST Study (Oxford – Fibrates in Aortic Stenosis)	Ethics Ref:	

NOTE: The term "life-threatening" in the definition of "serious" refers to an event in which the participant was at risk of death at the time of the event; it does not refer to an event which hypothetically might have caused death if it were more severe.

- Requires inpatient hospitalisation or prolongation of existing hospitalisation,
- Results in persistent or significant disability/incapacity, or
- Is a congenital anomaly/birth defect.
- Other important medical events*

*Other events that may not result in death, are not life threatening, or do not require hospitalisation, may be considered a serious adverse event when, based upon appropriate medical judgement, the event may jeopardise the participant and may require medical or surgical intervention to prevent one of the outcomes listed above.

9.2. Reporting Procedures for Serious Adverse Events

A serious adverse event (SAE) occurring to a participant should be reported to the REC that gave a favourable opinion of the study where in the opinion of the Chief Investigator the event was 'related' - resulting from administration of any of the research procedures and 'unexpected' in relation to those procedures. Reports of related and unexpected SAEs should be submitted within 15 working days of the Chief Investigator becoming aware of the event, using the HRA report of serious adverse event form.

All related AEs that result in a patient's withdrawal from the study or are present at the end of the study, should be followed up until a satisfactory resolution occurs. It will be left to the investigator's clinical judgment whether or not an AE is of sufficient severity to require the patient's removal from treatment. A patient may also voluntarily withdraw from treatment due to what he or she perceives as an intolerable AE. If either of these occurs, the patient would undergo an end of study assessment and be given appropriate care under medical supervision until symptoms cease or the condition becomes stable.

10. STATISTICS AND ANALYSIS

10.1. Description of Statistical Methods

Power and sample size calculations are based on our previous data¹³ on asymptomatic AS with MTG of $0.75 \pm 0.36\%$ vs $0.45 \pm 0.17\%$ in normal controls. In this current study, we acknowledge that pressure overload will not be reduced as patients will not undergo surgical intervention along with the uncertainty of change in MTG in moderate-severe AS patients.

Principal Investigator:	[name]	IRAS ID	252047
Short Title:	Ox-FAST Study (Oxford – Fibrates in Aortic Stenosis)	Ethics Ref:	

Accordingly, we have chosen a sample size of 62 (n=49 in treatment group, n=13 in placebo group) to detect a mean difference in MTG of 0.15% (compared to normals) instead of 0.3%, with SD 0.36 and 80% power.

In our proposed study, the primary focus is to detect physiological effect i.e. change in MTG before and after fenofibrate in the treatment group. Thus, our power calculations aim to detect expected changes from baseline in the treatment group alone, and the comparison between treatment group and placebo is not included in the calculation. The purpose of including the placebo group is to blind the study team during the data analysis process. Hence, we have higher number of patients in the treatment group compared to placebo.

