1. SYNOPSIS

Study Title	The effect of altering myocardial lipid content on cardiac physiology in patients with aortic stenosis	
Internal ref. no. / short title	Ox-FAST Study	
Study Design	Prospective randomised, double-blind, placebo-controlled	
Study Participants	Asymptomatic moderate to severe aortic stenosis patients	
Planned Sample Size	62	
Planned Study Period	36 months	
	Objectives	Outcome Measures
Primary	To assess change in myocardial triglyceride content (MTG) before and after 6 months of treatment with fenofibrate/placebo	Change in myocardial lipid content (lipid/water) measured by Proton magnetic resonance spectroscopy (¹ H-MRS)
Exploratory	To assess the following changes in cardiac physiology before and after treatment with fenofibrate/placebo 
 – LV strain – LV mass – Myocardial energetics – Peak oxygen consumption (VO₂ max) – Pericardial fat 	
 – Change in left ventricular strain measured by tagged CMR – Change in left ventricular mass measured by CMR – Change in Phospho-creatinine/ATP ratio (PCr/ATP) measured by Phosphorous magnetic resonance spectroscopy (³¹P-MRS) – Change in peak oxygen consumption measured by CPET – Change in pericardial fat volume measured by CMR

Principal Investigator:	[name]	IRAS ID	252047
Short Title:	Ox-FAST Study (Oxford – Fibrates in Aortic Stenosis)	Ethics Ref:	

Principal Investigator:	[name]	IRAS ID	252047
Short Title:	Ox-FAST Study (Oxford – Fibrates in Aortic Stenosis)	Ethics Ref:	

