4. OBJECTIVES AND OUTCOME MEASURES

The main objective is to study the effects of a fibrate drug, fenofibrate (a PPAR α agonist, a key regulator of lipid metabolism) on myocardial triglyceride content (MTG) and cardiac physiology including circumferential strain in patients with asymptomatic moderate-severe AS. We understand from various previous human ²⁴ and animal studies ^{25,27} that the effect of fenofibrate on cellular lipid metabolism becomes evident within six to fourteen weeks after treatment. In our pilot study¹³ eight months post AVR, both myocardial steatosis and strain were found to be significantly reduced. Based on this evidence, we believe that a study duration of 6 months will show expected physiological effect. Thus, we hypothesise that fenofibrate will result in steatosis regression and may result in changes in cardiac physiology in these patients over a period of 6 months.

Primary objective	Outcome measure	Timepoint(s) of evaluation
To assess change in myocardial triglyceride content (MTG) before and after 6 months of treatment with fenofibrate/placebo	Change in myocardial lipid content (lipid/water) measured by ¹ H-MRS	At baseline and 6 months
Exploratory objectives	Outcome measures	Timepoint(s) of evaluation

Principal Investigator:	[name]	IRAS ID	252047
Short Title:	Ox-FAST Study (Oxford – Fibrates in Aortic Stenosis)	Ethics Ref:	

To assess the following changes in cardiac physiology before and after treatment with fenofibrate/placebo
 
 – LV strain – LV mass – Myocardial energetics – Peak oxygen consumption (VO₂ max) – Pericardial fat 	
 – Change in left ventricular strain measured by tagged CMR – Change in left ventricular mass measured by CMR – Change in PCr/ATP ratio measured by ³¹P-MRS – Change in peak oxygen consumption measured by CPET – Change in pericardial fat volume measured by CMR 	
At baseline and 6 months

---	---	---------------------------------

5. STUDY DESIGN (*Appendix A and B*)

This research project is a single-centre, proof-of-concept cardiac magnetic resonance study to investigate the effect of altering MTG using fenofibrate on cardiac physiology in patients with asymptomatic moderate-severe AS. All patients will participate in a randomised, double-blind, parallel design placebo-controlled study for 6 months. The patients will be divided into two groups.

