- Group 1: This will include forty-nine patients who will receive treatment with fenofibrate for six months duration.
- Group 2: This group will act as controls, comprising of thirteen patients who will be randomly assigned to receive placebo for six months duration.

The study will be conducted in a single centre specialising in cardiac imaging. Both groups of patients will be identified from the large pool of outpatient clinics at John Radcliffe Hospital (Oxford) and district general hospitals in the region. Patients with asymptomatic moderate to severe aortic stenosis not planned for AVR or transcatheter aortic valve implantation (TAVI) will be reviewed against the eligibility criteria and invited to participate in the study.

Based on previous studies it is estimated that approximately 100 patients will need to be reviewed in total in order to identify 62 eligible patients. Vetting will continue until eligible patients have been randomised into both groups. A log of all participants recruited into the study will be maintained in the investigator site file (ISF) at the investigational site irrespective of whether they have been treated with investigational drug or not. Re-screening of patients who do not meet the inclusion/exclusion criteria will not be permitted, however assessments may be repeated within the screening period and the latest assessment prior to randomisation must always be used to assess eligibility.

Principal Investigator:	[name]	IRAS ID	252047
Short Title:	Ox-FAST Study (Oxford – Fibrates in Aortic Stenosis)	Ethics Ref:	

Subsequently, all eligible patients will undergo informed consent and baseline tests - bloods will be drawn for lipid profile, renal and liver function, glucose and free fatty acids, and urine for pregnancy test in women of child bearing potential. ¹H-MRS to assess MTG, ³¹P-MRS to assess myocardial energetics (PCr/ATP), standard cardiac magnetic resonance imaging to assess LV strain and LV mass, late gadolinium enhancement (fibrosis), physiological exercise assessments to measure VO₂ max and 6 minute walking distance. Patients will then be randomly assigned in a double blind fashion to either receive fenofibrate 200mg once daily or placebo. Randomisation will be done by local pharmacy using randomisation code list provided by Nottingham pharmacy. The subject and study investigators will be blinded to the randomisation schedule.

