10.3. Analysis of Outcome Measures

Based on literature data, the primary endpoint of change from baseline in MTG is regarded as normally distributed. The change from baseline of MTG after 6 months of treatment will therefore be analysed by paired student's t-test. The primary objective will be addressed by a one-sided test at level $\alpha = 0.05$. For continuous exploratory endpoints, the same model as the primary one will be used.

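### The primary analysis tests before-after change in the fenofibrate arm only, so it cannot separate a drug effect from change shared by both arms

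*Combined protocol and SAP*

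**What the plan says.** The Synopsis gives the design as "Prospective randomised, double-blind, placebo-controlled". Section 5 says of Group 2: "This group will act as controls, comprising of thirteen patients who will be randomly assigned to receive placebo". Section 4 states the hypothesis causally: "we hypothesise that fenofibrate will result in steatosis regression".

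The statistical sections take a different line. Section 10.1 sets the primary focus on before-after change in the treated group and says that "the comparison between treatment group and placebo is not included in the calculation". It gives the reason for the second arm as "The purpose of including the placebo group is to blind the study team during the data analysis process". Section 10.3 then specifies one analysis: "The change from baseline of MTG after 6 months of treatment will therefore be analysed by paired" Student's t-test, one-sided at 0.05. It adds: "For continuous exploratory endpoints, the same model as the primary one will be used".

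Section 10.3 does not name the arm tested. Sections 10.1 and 10.2 point to the fenofibrate arm. No section gives a between-arm test, estimate or interval for any efficacy endpoint, although Section 4 and Appendix B schedule MTG in both arms at baseline and six months.

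**The concern.** A before-after test in one arm asks whether MTG changed during treatment. It shows that fenofibrate caused the change only if MTG would otherwise have stayed the same for six months. The documents neither state nor justify that assumption, and Section 10.1 itself admits uncertainty about how MTG changes in these patients. Requiring stable medication before entry does not control what happens after entry.

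The error can go either way: a shared fall looks like a drug effect, and a shared rise masks one. The randomised placebo arm is the means of removing both, and the plan leaves it out of the primary inference. The same applies to the five continuous exploratory endpoints.

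A smaller point concerns the wording on power. Section 10.1 says "we have chosen a sample size of 62 (n=49 in treatment group, n=13 in placebo group") and attaches 80% power to that total. Its next paragraph limits the power to the treated arm, but no figure for the comparison with placebo appears anywhere.

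**Working it through.** **Inputs from the documents.** Difference 0.15, SD 0.36, power 80%, minimum n = 38, dropout 23%, allocation 49 and 13 (Sections 10.1 and 10.2); one-sided alpha 0.05 (Section 10.3).

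**Assumptions.** The 0.36 is the SD between patients in the earlier asymptomatic series. With SD 0.36 at each visit, it equals the SD of change only if the baseline to six-month correlation is 0.5, because SD of change = 0.36 × √(2(1 − r)). The one-sided test is taken to look for a fall, in line with the hypothesis. The sizes of shared change are assumed.

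**1. The plan's own figure.** For a one-sample t-test on change, the noncentrality is (δ/SD) × √n = (0.15/0.36) × √38 = 2.57. With 37 df and a one-sided critical value of 1.687, power is 81.0%, so 38 reproduces. A two-sided paired test would need 48. A two-group comparison with equal arms would need 72 per arm one-sided, or 91 to 92 two-sided. So 38 is a one-sided, single-arm, before-after figure, which settles which arm Section 10.3 means. Expected completers are 49 × 0.77 = 37.7 and 13 × 0.77 = 10.0, so about 38 and 10.

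**2. The planned test under shared change** (n = 38, SD of change 0.36, same formula with δ set to the net fall in the fenofibrate arm):

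| Drug effect | Shared change | Net fall | Probability significant |
|---|---|---|---|
| 0 | none | 0 | 5% |
| 0 | fall 0.05 | 0.05 | 21% |
| 0 | fall 0.10 | 0.10 | 51% |
| 0 | rise 0.05 | −0.05 | 0.6% |
| 0.15 | none | 0.15 | 81% |
| 0.15 | rise 0.05 | 0.10 | 51% |

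**3. The between-arm test under the same conditions.** In simulation (20,000 trials per case, 38 versus 10, correlation 0.5), a two-sided 5% ANCOVA rejected in 5.2%, 4.6% and 4.8% of trials in the three no-effect cases with shared change. For a true effect of 0.15 it rejected in 26.0% without the rise and 26.3% with it. Shared change drops out.

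**4. Precision of the between-arm comparison.** SE = SD × √(1/n₁ + 1/n₂), with √(1/38 + 1/10) = 0.355 and √(1/49 + 1/13) = 0.312. The SD is 0.36 for the change score and 0.36 × √(1 − 0.5²) = 0.312 for ANCOVA.

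| Analysis | Arms | SE | Power for 0.15, two-sided | One-sided | 95% CI half-width |
|---|---|---|---|---|---|
| Change score | 38 vs 10 | 0.128 | 21% | 31% | 0.26 |
| ANCOVA | 38 vs 10 | 0.111 | 26% | 38% | 0.22 |
| Change score | 49 vs 13 | 0.112 | 26% | 37% | 0.22 |
| ANCOVA | 49 vs 13 | 0.097 | 33% | 45% | 0.19 |

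For correlations from 0.3 to 0.7 with a visit SD of 0.36, two-sided ANCOVA power is 23% to 36% at 38 versus 10, and 28% to 45% at 49 versus 13. At correlation 0.5, the difference detectable with 80% two-sided power by ANCOVA is 0.32 at 38 versus 10 and 0.28 at 49 versus 13.

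**The case against.** The strongest reply is that this is a declared choice. Section 10.1 states the single-arm focus, the reason for the placebo group and the reason for unequal allocation. The study is called proof-of-concept, and its primary objective is worded as change before and after treatment. That explains the sample size, but it does not make a within-arm change attributable to the drug, which is what the hypothesis claims. Nor does leaving the comparison out of the power calculation prevent it from being analysed.

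The objective mentions fenofibrate and placebo together, so a paired test in each arm would also fit the text. Two such tests side by side are still not a comparison between arms.

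Several points stand:

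- No shared change is evidenced, so its size is unknown. Eligibility does not select on MTG, which gives regression to the mean little support here. The percentages show vulnerability, not expected error.
- Setting 81% beside 26% mixes a one-sided test with a two-sided one. On a one-sided basis, ANCOVA power at 38 versus 10 is 38%.
- The wording on 80% power is loose but is qualified in the next paragraph, so it is an editorial point.
- The between-arm comparison is weak, because the trial was not sized for it. That is a reason to report an estimate with its interval and to limit the claims, not to omit the randomised contrast.

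**Conclusion.** The concern holds and must be fixed. As written, the primary result can show that MTG changed during fenofibrate treatment, but it cannot show that fenofibrate changed it. This follows from the design of the analysis and needs no assumed number. Its practical size depends on how far MTG moves in both arms over six months, which the documents do not give. With 38 completers and an SD of change of 0.36, a shared fall of only 0.05, one third of the target difference, would raise the false-positive rate from 5% to 21%. The power and interval figures for the comparison with placebo also rest on that SD and, for ANCOVA, on the assumed correlation.

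**What to change.** Before database lock and unblinding:

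- **Section 10.3.** Add an ANCOVA of six-month MTG on randomised arm, adjusted for baseline MTG, in all randomised patients with a Visit 3 MTG measurement regardless of compliance. Report the adjusted difference with a two-sided 95% CI, and base any statement about fenofibrate's effect on it. Keep the paired results, by arm, labelled as change during treatment. Do the same for the five continuous exploratory endpoints.
- **Section 7.5.9.** This section removes patients below 80% compliance from the primary analysis and lets the investigator curtail their Visit 3 assessments. State which analysis set the rule applies to, and that the Visit 3 MTG measurement is needed for the between-arm analysis.
- **Section 10.1.** State that the 80% power applies only to within-arm change. Add that two-sided between-arm power for 0.15 is about 21% (change score) to 26% (ANCOVA) with 38 versus 10 completers, or 26% to 33% at 49 versus 13. Give the assumptions: SD of change 0.36 and, for ANCOVA, correlation 0.5. The range over other correlations could be added.

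**Cost.** Wording changes and one extra model per endpoint on measurements already scheduled, with no extra patients or visits. Patients with low compliance would need the Visit 3 MTG scan that can now be skipped. The drawback is precision: the ANCOVA interval at 38 versus 10 is about ±0.22, wider than the 0.15 target, so it will mainly bound the effect rather than confirm it. If the comparison is added only after unblinding, it will be post hoc.

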10.2. The Number of Participants

To detect a mean difference in MTG of 0.15% in the treatment group (i.e half the difference to normals when compared to our previous study) with a SD of 0.36, power of 80% and a $p < 0.05$, a minimum sample size of 38 will be required. We have allowed for 23% dropouts based on data from a previous randomised controlled trial on similar patient cohort⁴². Taking into account the 23% dropouts, the number of subjects required in the treatment group will be 49, and 13 in the placebo group, thus, taking the total number of recruited patients to 62 (n=49 for treatment group and n=13 for placebo).

10.3. Analysis of Outcome Measures

Based on literature data, the primary endpoint of change from baseline in MTG is regarded as normally distributed. The change from baseline of MTG after 6 months of treatment will therefore be analysed by paired student's t-test. The primary objective will be addressed by a one-sided test at level $\alpha = 0.05$. For continuous exploratory endpoints, the same model as the primary one will be used.

11. DATA MANAGEMENT

11.1. Access to Data

Direct access will be granted to authorised representatives from University of Oxford and Oxford University Hospital Trust for monitoring and/or audit of the study to ensure compliance with regulations.

11.2. Data Recording and Record Keeping

The study staff will ensure that the participants' anonymity is maintained. The participants will be identified only by a participant ID number on all study documents and any electronic

Principal Investigator:	[name]	IRAS ID	252047
Short Title:	Ox-FAST Study (Oxford – Fibrates in Aortic Stenosis)	Ethics Ref:	

database, with the exception of the CRF, where participant initials may be added. The code-break document which links participant ID with participant name and identifying information will be held on the medical sciences high security server, which is specifically designed for the storage of sensitive information. All documents will be stored securely and only accessible by study staff and authorised personnel.

All study data will be entered onto an Excel spreadsheet using the de-identified subject ID number in accordance with SOPs for data entry and validation. The name and any other identifying detail will not be included. Data will be analysed on Medcalc 9.5.2.0, SPSS or similar by delegated study investigators. As explained above, the participants will be identified only by a participant ID number on the CRF and any electronic database. All documents will be stored securely and only accessible by research staff and authorised personnel.

The Consent forms will be retained with the study master file and archived for up to 10 years after which they will be destroyed along with the study master file.

11.3. Data Blinding

We have delegated responsibilities within the study team such that the investigator analysing images will be blinded to blood test results and vice-versa so that any risk of unblinding through correlation of findings by a study team member is eliminated.

12. QUALITY ASSURANCE PROCEDURES

Data collected for the study may be reviewed for auditing and monitoring by authorised persons from the Sponsor (University of Oxford), regulatory authorities or the local host institution to make sure that the study is being carried out correctly. All investigators have a duty of confidentiality to research participants and nothing that could reveal their identity would be disclosed outside the research study team or site.

13. ETHICAL AND REGULATORY CONSIDERATIONS

13.1. Declaration of Helsinki

The Investigator will ensure that this study is conducted in accordance with the principles of the Declaration of Helsinki.

13.2. Guidelines for Good Clinical Practice

The Investigator will ensure that this study is conducted in accordance with relevant regulations and with Good Clinical Practice.

Principal Investigator:	[name]	IRAS ID	252047
Short Title:	Ox-FAST Study (Oxford – Fibrates in Aortic Stenosis)	Ethics Ref:	

13.3. Approvals

The protocol, informed consent form, participant information leaflet and any proposed advertising material will be submitted to an appropriate Research Ethics Committee (REC), and HRA for written approval.

The Investigator will submit and, where necessary, obtain approval from the above parties for all substantial amendments to the original approved documents.

